### 4.4 RE-SCREENING OF SUBJECTS

Subjects may be re-screened once, if approved by Sponsor, if the subjects' Screening culture is not positive for MAC or there is a substantial delay (longer than the Screening period) in obtaining the results from the microbiology labs. In the event that sputum culture results are not known by 8 weeks (Day -14), the Baseline (Day 1) visit should be scheduled as soon as possible in order to maintain the Screening window, and an extension of the Screening window to 14 weeks is allowed, if necessary. If sputum culture results are known prior to 8 weeks (Day -14),

Protocol Amendment #3 version: 22 February 2016

*This protocol is solely for the purpose of communicating information about the investigational drug between Insmmed Incorporated and study personnel. Information is not to be reproduced, abstracted or used for sharing of information for any other purpose, whatsoever, except with the written permission of Insmmed Incorporated.*

the Screening window of 10 weeks must be maintained. Subject will only be allowed to be re-screened only provided that all other entry criteria have been satisfied. Re-screened subjects will be assigned a new subject number within the EDC system. All Screening assessments must be repeated when a subject is re-screened.

#### **4.5 REPLACEMENT OF SUBJECTS**

Subjects may be replaced to ensure 261 subjects will be evaluable subjects by Month 6.

#### **4.6 DEFINITIONS OF CONVERTER AND COMPLETER**

A converter is defined as a subject who has 3 consecutive monthly MAC-negative sputum cultures at any time within the first 6 months of the study.

Relapse or recurrence is defined as having MAC-positive sputum cultures in liquid broth media (agar negative) for 3 or more consecutive months, or having 1 MAC-positive sputum culture on solid media (agar positive) after achieving culture conversion.

A non-converter is defined as a subject who does not have 3 consecutive monthly MAC-negative sputum cultures at any time within the first 6 months of the study.

A completer for this study will be defined as follows:

1. A converter who successfully completes 12 months on the same treatment regimen beginning from the first of 3 negative cultures that defined conversion and successfully completes the 12 months off-treatment EOS follow-up visit.
2. A non-converter who successfully completes all dosing and protocol requirements up to and including the Month 6 study visit.

### **5 STUDY TREATMENTS**

#### **5.1 INVESTIGATIONAL STUDY DRUG**

Liposomal amikacin sulfate is encapsulated in liposomes composed of DPPC and cholesterol (2:1 w:w lipid ratio) formulated as a suspension at a targeted concentration equivalent to 70 mg

Protocol Amendment #3 version: 22 February 2016

*This protocol is solely for the purpose of communicating information about the investigational drug between Insmmed Incorporated and study personnel. Information is not to be reproduced, abstracted or used for sharing of information for any other purpose, whatsoever, except with the written permission of Insmmed Incorporated.*

amikacin/mL in 10 mL of water for injection (**Error! Reference source not found.5-1**). The total lipid to drug ratio is 0.57 to 0.77 w:w (weight to weight).

**Table 5-1 Composition of Liposomal Amikacin Sulfate**

Ingredient	Quality Grade	Mg/mL
Amikacin base (amikacin sulfate)	EP/USP	70
Cholesterol	HP a	15.7
Dipalmitoylphosphatidylcholine (DPPC)	In-house	31.5
Sodium chloride	USP/EP/JP	12
Sodium hydroxide	USP/EP/JP	QS to adjust pH
Water for injection	USP/EP/JP	QS

Abbreviations: EP, European Pharmacopeia; HP, High Purity; JP, Japanese Pharmacopeia; NF, National Formulary, USP, United States Pharmacopeia.

a HP grade meets or exceeds all requirements for cholesterol USP/NF/EP.

## 5.2 REFERENCE STUDY DRUG

None

## 5.3 ADMINISTRATION OF STUDY DRUG

LAI is administered daily by inhaling drug product that has been aerosolized in an eFlow nebulizer over approximately 14 minutes. Study drug will be administered daily by the subject except two days prior to a scheduled study visit when sputum is collected (refer to [Section 7.1.1](#)). The day of study visit, when sputum is collected, the study drug will be administered at the study

Protocol Amendment #3 version: 22 February 2016

*This protocol is solely for the purpose of communicating information about the investigational drug between Insméd Incorporated and study personnel. Information is not to be reproduced, abstracted or used for sharing of information for any other purpose, whatsoever, except with the written permission of Insméd Incorporated.*

Confidential

site by study personnel. Written directions for preparing and administering the study drug will be provided to subjects.

### **Dose Interruption**

If a subject experiences local respiratory events such as, but not limited to, dysphonia, oropharyngeal pain, and cough while taking LAI that may be distressing to the subject, short interruptions of LAI may be necessary and are permitted. As the frequency of these local respiratory events decreased with continued use in prior LAI studies, it is recommended that LAI is reintroduced after a short interruption of dosing when symptoms subside. Please contact the medical monitor to discuss.

## **5.4 SELECTION OF DOSES**

It is intended that all subjects randomized to the LAI plus multi-drug regimen will receive the contents of 1 vial, 590 mg of LAI, of nebulized study drug.

Subjects who cannot tolerate 590 mg of LAI QD will be discontinued from LAI (with the exception of short interruptions as discussed in [Section 5.3](#)); the dose of LAI will not be changed during the study.

## **5.5 SELECTION OF TIMING OF ADMINISTRATION**

Study drug may be administered QD around the same time each day, any time of day, in the fasted or as-fed condition.

## **5.6 BLINDING**

None

## **5.7 STUDY KIT**

Subjects will receive kits containing vials of LAI, the handset/nebulizer, and controller.

Protocol Amendment #3 version: 22 February 2016

*This protocol is solely for the purpose of communicating information about the investigational drug between Insmmed Incorporated and study personnel. Information is not to be reproduced, abstracted or used for sharing of information for any other purpose, whatsoever, except with the written permission of Insmmed Incorporated.*

Confidential

## **5.8 DRUG SUPPLY**

The active ingredient, amikacin sulfate, is manufactured in accordance with cGMPs by ACS DOBFAR S.p.A.

### **5.8.1 Packaging**

LAI is provided as a unit dose consisting of a 10 mL Type I clear borosilicate glass vial with a 20 mm finish using a closure system consisting of a 20 mm bromobutyl stopper and a 20 mm aluminum flip-off tear-off combination seal.

### **5.8.2 Labeling**

Vials of study drug will be labeled as shown in [APPENDIX 2](#).

### **5.8.3 Storage**

At the site, LAI must be stored at 2°C to 8°C (36°F to 46°F) in a secured place with restricted access. Do not freeze.

### **5.8.4 Compliance and Drug Accountability**

Drug accountability will be recorded at each study visit by count of study drug at each study visit.

A subject will be considered non-compliant with study drug if treatment adherence is less than 80% or more than 120% unless instructed by the Investigator to interrupt dosing for safety reasons ([Section 5.3](#)).

### **5.8.5 Dispensing of Study Drug**

Study drug (LAI) will be shipped to the study site after the first subject is screened. Patients randomized to the LAI treatment will be dispensed adequate study drug at each visit to allow for daily dosing, including extra supply for potential study visit scheduling delays.

Protocol Amendment #3 version: 22 February 2016

*This protocol is solely for the purpose of communicating information about the investigational drug between Insmmed Incorporated and study personnel. Information is not to be reproduced, abstracted or used for sharing of information for any other purpose, whatsoever, except with the written permission of Insmmed Incorporated.*

### 5.8.6 Disposition and Reconciliation of Study Drug

Drug accountability records will be maintained for all clinical supplies. All transactions will be recorded on the drug accountability records including shipment receipts, study subject doses, and transfers to other locations within the study site. All transactions will be recorded on a real-time basis.

The pharmacy will maintain detailed documentation of the number and identification of vials with copies of these documents to be provided to the Sponsor at the end of the study. All used and unused boxes of study drug will be maintained by the site until inventoried by the study monitor. Upon completion of the drug inventory by the study monitor, used and any unused vials will be disposed of in accordance with instructions provided to sites and according to site destruction policies. Documentation of destruction should be provided to the Sponsor.

Accountability of the PARI eFlow® nebulizer will be maintained and tracked at the site. Subjects must return the nebulizers to the study site at the end of treatment. Additional instructions for handling the disposal or return of the devices will be provided to the sites and according to site destruction policies.

## 5.9 CONCOMITANT MEDICATIONS

Throughout the duration of the study, subjects should continue on the same, multi-drug (at least 2 antibiotics), anti-mycobacterial regimen. The regimen should be based on the 2007 ATS/IDSA Guidelines or respective local guidelines, and should not change during the treatment period except for safety concerns or if “rescue” anti-mycobacterial therapy is required. Any subject who has to have “rescue” medication will be discontinued. All NTM treatment should stop at the EOT visit. No NTM treatment should be given during the safety follow-up period.

Where allowed, and if approved by IRB/EC, the sponsor will provide reimbursement of the multi-drug anti-mycobacterial regimen for as long as the patient participates in the study and is adherent to all protocol requirements. These drugs may include, but are not limited to: azithromycin, clarithromycin, clofazimine, ethambutol, ethionamide, rifabutin, and rifampicin.

Protocol Amendment #3 version: 22 February 2016

*This protocol is solely for the purpose of communicating information about the investigational drug between Insmmed Incorporated and study personnel. Information is not to be reproduced, abstracted or used for sharing of information for any other purpose, whatsoever, except with the written permission of Insmmed Incorporated.*

## 5.10 PROHIBITED MEDICATIONS

Subjects are prohibited from using any inhaled antibiotics and any aminoglycosides with activity against MAC from 28 days before Day 1, and should not initiate these drugs during the study period unless clinically indicated as determined by the Investigator. If a subject requires an inhalational antibiotic for medical management of an acute pulmonary exacerbation secondary to Gram-negative bacteria during the study, then LAI should be interrupted during the course of that inhaled antibiotic treatment and until the acute event has resolved. Inhaled antibiotics such as tobramycin that do not have activity against MAC are permitted. Administration of LAI should begin again after the inhaled antibiotic is stopped and the acute event has resolved. During the course of an inhaled antibiotic treatment, the subject will remain in the study and complete all remaining study visits if possible. Exceptions include treatment with IV amikacin (or nebulized IV amikacin solution) and other aminoglycosides with activity against MAC, such as streptomycin or kanamycin. Such aminoglycosides for the treatment of NTM lung infection will be considered a “rescue” medication. If the Investigator believes that any of the aforementioned prohibited medications are necessary they must discuss these with the medical monitor and the subject will discontinue study drug and/or the study. Any questions about prohibited medications should be discussed with the medical monitor for the study.

## 5.11 PRECAUTIONARY MEDICATIONS

Treatment with oral or IV antibiotics (other than the subject’s stable anti-mycobacterial regimen) for acute pulmonary exacerbations or acute infection is allowed as determined by the Investigator; the reason for use must be documented in the eCRF (electronic case report form). Intra-muscular antibiotics that do not have activity against MAC (see prohibited medications) are permitted and must be documented in the eCRF.

Chronic anti-inflammatory therapy (e.g., high-dose ibuprofen, prednisone  $\leq$  10 mg/day or the equivalent) is permitted if the regimen remains unaltered for at least 28 days preceding Day 1 and throughout the study. The doses should not change except for safety reasons or as needed for medical management of the subject.

Although systemic exposure to amikacin is low after LAI administration, precaution should be taken if subjects require the following systemic medications that may have possible interactions

Protocol Amendment #3 version: 22 February 2016

*This protocol is solely for the purpose of communicating information about the investigational drug between Insmmed Incorporated and study personnel. Information is not to be reproduced, abstracted or used for sharing of information for any other purpose, whatsoever, except with the written permission of Insmmed Incorporated.*

with amikacin: potent diuretics (such as ethacrynic acid and furosemide), beta lactam antibiotics (such as penicillins and cephalosporins); bisphosphonates; platinum compounds and thiamine.

Bronchodilator therapy is allowed. Subjects who develop bronchospasm may be pre-treated with a bronchodilator before study drug administration.

**Table 5-2 List of Examples of Precautionary Medications**

Name of Drug, etc.	Clinical Symptoms/ Treatment	Mechanism/ Risk Factor(s)
Potentially nephrotoxic blood substitutes such as Dextran Hydroxyethyl starch, etc.	Since there is a risk that nephrotoxicity occurs or is aggravated, concomitant use should be avoided.  When nephrotoxicity occurs, discontinue drug and implement appropriate treatment such as renal dialysis, etc.	The mechanism of action is not completely clear but there are reports that the combination leads to deposits of aminoglycoside antibiotics in blood and to vacuolization of the proximal tubular epithelium.
Loop diuretics Ethacrynic acid Furosemide Azosemide, etc.	Since both drugs may cause or aggravate nephro- and ototoxicity, concomitant use should be avoided	The mechanism of action is not completely clear but there are reports that the combination leads to increased blood concentration and renal deposits of aminoglycoside antibiotics
Nephrotoxic and ototoxic drugs such as Vancomycin, Enviomycin, Platinum-containing anti-cancer drugs (cisplatin, carboplatin, nedaplatin), etc.	Since both drugs may cause or aggravate nephro- and ototoxicity, concomitant use should be avoided	Both drugs are nephrotoxic/ ototoxic but the mechanism of action of the interaction is not known.

Protocol Amendment #3 version: 22 February 2016

*This protocol is solely for the purpose of communicating information about the investigational drug between Insmmed Incorporated and study personnel. Information is not to be reproduced, abstracted or used for sharing of information for any other purpose, whatsoever, except with the written permission of Insmmed Incorporated.*

Anesthetics Muscle relaxants Tubocurarine Pancuronium bromide Tolperisone Botulinum type A toxin products, etc.	Risk of respiratory suppression. If respiratory suppression occurs, administer choline esterase inhibitor or calcium preparation, etc. as appropriate.	Both drugs have a neuro-muscular inhibitory effect. Concomitant use will aggravate this effect.
Nephrotoxic drugs Cyclosporine A Amphotericin B, etc.	Risk that renal impairment occurs or is aggravated	Both drugs are nephrotoxic but the mechanism of the interaction is not known.

## 5.12 DISCONTINUATION OF STUDY DRUG AND/OR STUDY PARTICIPATION

1. The Investigator may discontinue study drug and/or study participation in the interest of subject safety. The Investigator must identify specific AEs (laboratory abnormality, intercurrent illness, other medical condition or situation) that result in premature discontinuation of study drug and/or study participation in the eCRF.
2. A subject who withdraws consent to receive study drug may be followed up according to the protocol visit schedule. All attempts must be made to conduct an EOT visit ([Section 6.7](#)).
3. Subjects who meet the following criteria established by Hy's law will be discontinued from the study: alanine aminotransferase or aspartate aminotransferase  $\geq 3$  ULN AND total bilirubin  $> 2$  ULN.
4. Subjects who need "rescue" medication as described in [Section 5.9](#) will be discontinued.
5. Subjects who become pregnant will be discontinued from the study and followed until the pregnancy is concluded.
6. Administration of study drug will be discontinued to all subjects seen by an Investigator who terminates participation in the study prematurely.

Protocol Amendment #3 version: 22 February 2016

*This protocol is solely for the purpose of communicating information about the investigational drug between Insmmed Incorporated and study personnel. Information is not to be reproduced, abstracted or used for sharing of information for any other purpose, whatsoever, except with the written permission of Insmmed Incorporated.*

7. Administration of study drug will be discontinued to all subjects if the study is terminated.

The Investigator must contact the medical monitor immediately before discontinuing a subject from study drug and/or study participation if possible, or no later than 1 business day after the event. When a subject is prematurely discontinued from study drug, the subject will be given the option to continue in the study, off study drug, until their Month 8 visit (except for subjects enrolled at sites in Japan. All subjects at sites in Japan who discontinue study drug will also discontinue study participation). When a subject is prematurely discontinued from study drug and/or study participation, the Investigator will clearly document the reason in the medical record and complete the appropriate eCRF page describing the reason for discontinuation. If the subject completes all study procedures (including those who discontinued study drug but remain in the study), up to and including the Month 6 study visit, and sputum results indicate non-conversion or relapse/recurrence, they will be invited to participate in a separate open-label study of LAI (Study INS-312), provided all entry criteria have been met for that study. Any subject who discontinues the study prior to the Month 6 study visit will not be eligible to participate in the separate open-label study of LAI (INS-312).

In the event that a subject is withdrawn from the study treatment because of an AE, the subject should be followed and treated by the Investigator until the abnormal parameter or symptom is resolved or stabilized. It is up to the Investigator to determine and document that the AE is either resolved or that it has reached a stable state, after which no further follow-up is necessary.

If a subject fails to complete scheduled assessments in the study, the Investigator must determine the reasons and the circumstances as completely and accurately as possible. "Lost to follow-up" should be marked only in an exceptional case when all documented attempts to reach the subject by the Investigator or other staff members were unsuccessful.

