## 3 INVESTIGATIONAL PLAN

### 3.1 STUDY DESIGN

The Screening window allows time for sputum culture results, susceptibility by minimum inhibitory concentration (MIC) determination, and scheduling of Screening assessments. Any delay in obtaining microbiological results and MICs must be reported to the Sponsor immediately and documented within the study source documents. In the event that sputum culture results are not known by 8 weeks (Day -14), the Baseline (Day 1) visit should be scheduled as soon as possible in order to maintain the Screening window, and an extension of the Screening window to 14 weeks is allowed, if necessary. If sputum culture results are known prior to 8 weeks (Day -14), the Screening window of 10 weeks must be maintained. Once Screening assessments are complete and sputum culture results are known, eligible

Protocol Amendment #3 version: 22 February 2016

*This protocol is solely for the purpose of communicating information about the investigational drug between Insmid Incorporated and study personnel. Information is not to be reproduced, abstracted or used for sharing of information for any other purpose, whatsoever, except with the written permission of Insmid Incorporated.*

Confidential

subjects will be randomized 2:1 to LAI administered QD plus a multi-drug regimen or a multi-drug regimen alone. The primary endpoint will assess culture conversion by Month 6.

Sputum culture results will only be available to the site after the Month 6 sputum result is known, in time for the Month 8 visit. At Month 8 (-28 to +7 days), after all sputum culture results are known, up to and including Month 6, subjects will be assessed as converters or non-converters.

All converters will remain in Study INS-212 (Section 4.6). All converters who, after culture conversion, subsequently have MAC-positive sputum cultures in liquid broth media (agar negative) for 1 or 2 consecutive months only, will also remain in Study INS-212. These subjects will continue on their randomized treatment regimen until they complete a total of 12 months of treatment (EOT), starting from the first of 3 negative cultures that defines culture conversion. These subjects will return after the EOT visit for 28 day, 3, 6 and 12 months off-treatment follow-up visits. The 12 months off-treatment follow-up visit will be the end of study (EOS) visit. No NTM treatment will be administered during the off-treatment phase.

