### **5.12.1 Procedures for Discontinuation**

If a subject prematurely discontinues the study prior to the Month 12 (Visit 11) visit (excluding subjects enrolling in INS-312), the subject will have:

- EOT visit

Protocol Amendment #3 version: 22 February 2016

*This protocol is solely for the purpose of communicating information about the investigational drug between Insmmed Incorporated and study personnel. Information is not to be reproduced, abstracted or used for sharing of information for any other purpose, whatsoever, except with the written permission of Insmmed Incorporated.*

- Telephone contact 28 days after the EOT visit for safety follow-up
- Telephone contact at Month 12 (time point from Baseline) for safety follow-up (if not coinciding with the 28 day after EOT telephone contact)
- Telephone contact 12 months after the EOT visit for vital status and safety follow-up

If a subject prematurely discontinues the study on or after the Month 12 visit, the subject will have:

- EOT visit
- Telephone contact 28 days after the EOT visit for safety follow-up
- Telephone contact 12 months after the EOT visit for vital status and safety follow-up

If a subject prematurely discontinues the study during the off-treatment phase (after completion of 12 months of treatment), the subject will have:

- Telephone contact at the 12 Month Safety Follow-Up visit for vital status and safety follow-up

Subjects who are part of the sputum PK subset who discontinue LAI at any time point will have to return for clinic visits 28 days and 3 months off-LAI for sputum PK and sputum culture collection.

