Supportive ANCOVA analyses of the change from Baseline to Month 6 in 6MWT distance with treatment arm and the randomization strata as factors, and the Baseline 6MWT distance as a covariate will also be performed for both the ITT and the PP populations. In the ANCOVA analysis for the ITT population, the last-observation-carried-forward method will be used to handle the missing data.

The changes from Baseline to Month 8 (exploratory endpoint), EOT, and 3 months off-treatment (exploratory endpoint) in 6MWT distance will be analyzed for the ITT population using the similar mixed-effects model for repeated measures (MMRM) with an unstructured covariance matrix implemented with SAS MIXED procedure over all post-randomization visits.

Kaplan-Meier estimates for the distribution of time to culture conversion will be constructed for treatment arms. The treatment comparison will be made using the stratified log rank test for the ITT population. The estimated median time to culture conversion for each treatment arm will be presented. The time to culture conversion will also be analyzed using Cox regression model to estimate hazards ratio.

The proportion of subjects achieving culture conversion with sustainability at the EOT and the proportion of subjects achieving culture conversion with durability after 3 months off-treatment will be analyzed for both the ITT and PP populations similarly using the Cochran-Mantel-Haenszel test stratified by smoking status and prior multi-drug regimen. Subjects who relapse, have “rescue” medication and/or die before reaching EOT for sustainability and 3 months off-treatment for durability will be considered as failure to achieving culture conversion.

Protocol Amendment #3 version: 22 February 2016

*This protocol is solely for the purpose of communicating information about the investigational drug between Insmmed Incorporated and study personnel. Information is not to be reproduced, abstracted or used for sharing of information for any other purpose, whatsoever, except with the written permission of Insmmed Incorporated.*

The change from Baseline (Day 1) to Month 6 in SGRQ total score and the SGRQ – Part 2 subdomain (exploratory endpoint) will be analyzed for the ITT population similarly using the same MMRM method as the analysis of the change from Baseline to EOT in 6MWT distance.

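### The Month 8 limit on follow-up after stopping LAI conflicts with keeping all converters in the study and, if applied, loses durability cultures unequally by arm

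*Protocol*

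**What the plan says.** Three rules in the protocol cover a converter who stops LAI.

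- Section 3.1: "All converters will remain in Study INS-212". They continue the randomised regimen to 12 months from the first negative culture (EOT), then return at 28 days and 3, 6 and 12 months off treatment.
- Section 5.12, main text: after premature discontinuation of study drug, "the subject will be given the option to continue in the study, off study drug, until their Month 8 visit". Converters are not excepted. Japan is stricter: "All subjects at sites in Japan who discontinue study drug will also discontinue study participation".
- Section 5.12, item 2: "A subject who withdraws consent to receive study drug may be followed up according to the protocol visit schedule".

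Section 5.8.5 identifies study drug as LAI: "Study drug (LAI) will be shipped to the study site after the first subject is screened". Section 5.9 allows the background regimen to change for safety and attaches no exit from the study to such a change.

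Section 6.7 gives anyone who stops study drug early the EOT procedures, which include a sputum culture. For subjects who leave before the off-treatment phase, Section 5.12.1 then provides telephone contacts only, the first being "Telephone contact 28 days after the EOT visit for safety follow-up". The exception is the sputum PK subset, whose members return 28 days and 3 months off LAI for sputum PK and culture.

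Section 9.6.2 analyses sustainability and durability in the ITT and PP populations. Subjects who relapse, take rescue medication or "die before reaching EOT for sustainability and 3 months off-treatment for durability will be considered as failure to achieving culture conversion". Stopping LAI and leaving the study are not on that list.

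**The concern.** Durability needs a culture 3 months after the end of treatment. Under the main text of Section 5.12, a converter who gives up LAI, perhaps for tolerability, but stays on the multi-drug regimen is out of the study months before that culture falls due. Section 3.1 would keep the same subject in. Item 2 would also allow it, but only when the stop came through withdrawn consent to study drug. Sites cannot follow all three rules.

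The Month 8 limit is triggered by stopping LAI, which only one arm receives. A control converter whose background drug is changed for safety keeps full follow-up. The chance of missing the durability culture therefore depends on arm and on tolerability of LAI. Some stopping is to be expected: Section 5.4 allows no dose change and, short interruptions aside, takes subjects who cannot tolerate the dose off LAI. A statistical analysis plan can choose how to score these subjects, but it cannot recover cultures that were never collected.

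**Working it through.** **The rules on one case.** Take an LAI subject with negative cultures at Months 2, 3 and 4 who stops LAI at Month 5 and stays on the multi-drug regimen. By Section 3.1, EOT is at Month 2 + 12 = Month 14 and the durability culture at Month 14 + 3 = Month 17. By the main text of Section 5.12 the subject leaves at Month 8 at the latest, with an early EOT culture and then telephone calls. For a converter who stops LAI after Month 8, the main text offers no further stay; only item 2 could apply. The primary endpoint (conversion by Month 6) is not touched by the Month 8 limit.

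**Inputs.** From Section 9.1: durability 16% (LAI) and 4% (control), 174 and 87 subjects, Fisher's exact test, two-sided 0.05, power at least 83%. From Section 3.6.1: about 351 randomised, so 351 × 2/3 = 234 on LAI. Assumed, because the protocol gives no figure: 10%, 20% or 30% of LAI subjects stop LAI, and those who stop would have been durable at between the control rate (4%) and the LAI rate (16%).

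**The plan's own figure.** Exact enumeration of Fisher's test with 0.025 in each tail gives 83.2%, which reproduces the stated power. The other common two-sided version, which sums tables no more likely than the observed one, gives 85.7%, also consistent with at least 83%.

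**Durable outcomes lost.** Number lost = 234 × share stopping × durable rate among stoppers. LAI rate if these are scored as failures = 16% − share stopping × durable rate among stoppers. The starting point is 234 × 16% = 37 durable LAI subjects.

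| Share stopping LAI | Lost (stoppers durable at 4%) | Lost (at 16%) | LAI rate (at 4%) | LAI rate (at 16%) |
|---|---|---|---|---|
| 10% | 0.9 | 3.7 | 15.6% | 14.4% |
| 20% | 1.9 | 7.5 | 15.2% | 12.8% |
| 30% | 2.8 | 11.2 | 14.8% | 11.2% |

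These counts treat every stopper as lost. Follow-up under item 2 or in the PK subset would reduce them.

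**Power.** On the protocol's 174 and 87, with control held at 4%, the 83.2% falls to 78.3% at an LAI rate of 15.2%, 72.6% at 14.4%, 59.0% at 12.8% and 43.3% at 11.2%. Had the same share of durable converters been lost in both arms, power would be 77.7%, 70.9% and 62.6% at 10%, 20% and 30%. The gap between the two sets is the part due to unequal loss. The protocol's power base is 174 and 87; an ITT analysis of all 351 would start from a larger number, so these powers illustrate the direction and relative size.

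**If stoppers were dropped instead.** With a 20% conversion rate, 174 × 20% = 34.8 LAI converters, of whom 10-30% is 3.5 to 10.4. Removing them from the denominator gives an LAI rate of 14.7% to 11.9% if they are as durable as other converters, or 16.3% to 17.0% if none would have been durable. The sign of the bias would then depend on the unknown outcomes.

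**The case against.** The strongest reply is that Section 5.12 does not settle the matter. Section 3.1 and item 2 point the other way, so the Month 8 limit may not prevail. That stands: the loss is conditional on the limit being applied, and the certain defect is the conflict.

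A reader might infer that only the LAI arm loses converters. The documents do not support that. Section 4.3 lets subjects in either arm leave through an adverse event, noncompliance, withdrawn consent, rescue or investigator judgement, and Section 5.12.1 then gives both arms the same telephone contacts. Usage of study drug is also loose: footnote l of Table 3-1 has it dispensed to all subjects. What remains is that stopping LAI is an additional route out with no written counterpart in control.

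A reader might also infer that sustainability suffers equally. Section 2.2 defines it over 12 months on treatment, and Section 3.1 has converters continue the randomised regimen, so someone who stops LAI arguably fails by definition. The text does not say whether the multi-drug regimen alone counts as treatment, but durability is clearly the stronger case. It could be argued that durability too presupposes a completed course, which is a choice of estimand. Section 9.6.2 does not make that choice, and without cultures no other choice can be examined.

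On scoring, ITT is all randomised subjects, and Section 9.6.1 counts subjects not evaluable for conversion because of missing cultures as non-converters. Scoring as failure is the likelier reading, and dropping subjects finds no support. The consequence is then a conservative LAI estimate and lost power, not a false claim of benefit.

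Finally, the PK subset is at least 60 LAI subjects (Section 7.4.1), or 60/234, about a quarter. Their return visits show that such cultures are feasible, but they are timed from stopping LAI and not from the end of all treatment.

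**Conclusion.** The point holds for durability. The main text of Section 5.12, its item 2 and Section 3.1 give different follow-up for a converter who stops LAI. If the Month 8 limit is applied, no culture at 3 months off treatment is collected for that subject outside the sputum PK subset. The loss is unequal by arm because the limit acts through LAI, but it is not confined to the LAI arm. Sustainability is less affected, and early stoppers do have an EOT culture; what they lack is the culture at the scheduled 12-month EOT and those after it.

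Assuming 10-30% stop LAI and would be durable at 4-16%, about 1 to 11 of 234 LAI subjects lose a durable outcome. If these are scored as failures, the LAI rate falls from 16% to between 15.6% and 11.2%. The stopping share is an assumption, and the upper end takes stoppers to be as durable as everyone else with none followed by another route. The matter should be corrected: durability is the second secondary endpoint and has its own power statement.

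**What to change.** Reconcile Section 3.1, both parts of Section 5.12 and Section 5.12.1 so that converters in both arms keep the scheduled sputum culture visits whether or not they still take LAI: Month 8, Month 12, EOT, and 28 days, 3, 6 and 12 months off treatment. Count the off-treatment visits from the actual end of all NTM treatment, so that 3 months off treatment means the same in both arms, and distinguish the visit made on stopping LAI early from the scheduled EOT visit. Section 6.8, whose heading limits it to subjects completing 12 months of treatment, needs the matching change. Non-converters and subjects who relapse still exit at Month 8, as now.

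If the Japan exit rule has to stay, acknowledge the remaining loss there.

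This concerns data collection only and leaves treatment decisions to the investigator. The cost is protocol wording and a few sputum visits, already in the schedule, for a small number of converters.
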